### **6.8.4      Other Observations Related to Safety**

#### **6.8.4.1      ECG Measurements**

ECG data will be summarized at the final follow-up evaluation using descriptive statistics for the safety population in total, as well as by treatment received in ACN03/ACN04. Descriptive statistics will be provided for the following ECG parameters, for observed values and changes

from Baseline: heart rate (HR), RR duration, QRS duration, PR duration, QT duration and QTc duration. Change from Baseline in ECG abnormalities will also be summarized using shift tables at the final evaluation visit.

Shift tables will be based on the following categories:

- PR Interval: < 100 msec, 100 – 220 msec and > 220 msec;
- QRS Interval: < 50 msec, 50 – 110 msec and > 110 msec;
- QTcF Interval: < 450 msec, 450 – 500 msec and > 500 msec.

For subjects receiving Olumacostat Glasaretil Gel, 5.0% in ACN03/ACN04, the final follow-up analysis visit will be Week 48/ET. For subjects receiving Olumacostat Glasaretil Gel, Vehicle in ACN03/ACN04, the final follow-up analysis visit will be Week 36/ET.

#### **6.8.4.2 Vital Signs**

Vital signs will be presented by analysis visit as observed values and changes from Baseline using descriptive statistics. Specifically, analysis visits to be summarized include Baseline and Weeks 4, 8, 12, 16, 20, 24, 28, 32, 36, 40, 44, and 48.

#### **6.8.4.3 Physical Examination**

Physical examination data will be presented in a by-subject listing.

#### **6.8.4.4 Local Skin Reactions (LSRs)**

Local Skin Responses (LSRs) include erythema, peeling, dryness, burning/stinging and pruritus. These will be scored as 0 (None), 1 (Mild), 2 (Moderate) or 3 (Severe). LSRs will be summarized by analysis visit using descriptive statistics. Specifically, analysis visits to be summarized include Baseline and Weeks 4, 8, 12, 16, 20, 24, 28, 32, 36, 40, 44, 48. Each subject's worst post-baseline grade for each LSR will also be summarized. Additionally, the number of subjects who experience mild, moderate or severe LSRs post-baseline will be presented. By-subject listings of all LSRs, as well as subjects with any severe LSRs will be included.

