A comparison of subjects with a 2-grade improvement in IGA score with or without a concurrent IGA score of clear or almost clear at Weeks 4, 8, and 12 showed that in each treatment group at each IGA assessment time point, most subjects who achieved a 2-grade improvement in IGA score also had an IGA score of clear or almost clear.

Pharmacokinetic (PK) results, assessed in a subset of subjects, showed that plasma concentrations of olumacostat glasaretil on Day 1 were undetectable for all but one subject, who had a plasma concentration of 0.304 ng/mL at one time point (2 hours post-dosing). Plasma concentrations of olumacostat glasaretil at Week 8 were undetectable for all tested subjects. Plasma concentrations of TOFA on Day 1 were undetectable in most subjects, but detectable in a few subjects in each dose group, with values ranging from 0.101 to 1.02 ng/mL. Plasma concentration of TOFA at Week 8 were undetectable for most subjects in the Olumacostat Glasaretil Gel QD dose groups, but detectable in a few subjects, with values ranging from 0.100 to 0.299 ng/mL. In the Olumacostat Glasaretil Gel, 7.5% BID group, approximately half of the tested subjects had detectable TOFA levels at each time point, with mean values ranging from 0.156 to 0.340 ng/mL.

The most common AEs reported during the study were nasopharyngitis, upper respiratory tract infection, and application site pruritus. Most AEs were mild or moderate in severity. Erythema was the most common LSR. Laboratory values, vital signs, and ECGs measured at the end of the study were generally consistent with baseline values, with no clinically significant trends.

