### **6. STATISTICAL AND ANALYTICAL PLANS**

#### **6.1 General Methodology**

All statistical processing will be performed using SAS® unless otherwise stated. Data will be summarized using descriptive statistics. No inferential testing or imputations for missing data will be performed.

Categorical variables will be tabulated with frequencies and percentages. Continuous variables will be tabulated with mean, median, SD, and range (minimum and maximum).

Reported AEs and prior and concomitant procedures and therapies will be classified on the basis of Medical Dictionary for Regulatory Activities (MedDRA) terminology. Concomitant medications will be classified on the basis of World Health Organization Drug Dictionary (WHO-DDE) terminology.

The following data will be imported from ACN03/ACN04 (Baseline defined in section 6.1.2):

Subjects receiving Olumacostat Glasaretil Gel, 5.0% in ACN03/ACN04:

- Demographic information: age, gender, race and ethnicity
- Prior and Concomitant medications
- Adverse events
- Local skin reactions (Baseline and Weeks 4, 8, 12)
- Vital signs and weight (Baseline and Weeks 4, 8, 12)
- Investigator Global Assessment of acne (Baseline and Week 12)
- Acne Patient Self-Questionnaire (Baseline and Week 12)
- Laboratory evaluations: hematology, serum chemistries and urinalysis (Baseline)
- 12-lead ECG (Baseline)

Subjects receiving Olumacostat Glasaretil Gel, Vehicle in ACN03/ACN04:

- Demographic information: age, gender, race, and ethnicity
- Prior and Concomitant medications
- Adverse events
- Local skin reactions (Baseline)
- Vital signs and weight (Baseline)
- Investigator Global Assessment of acne (Baseline)
- Acne Patient Self-Questionnaire (Baseline)
- Laboratory evaluations: hematology, serum chemistries and urinalysis (Baseline)
- 12-lead ECG (Baseline)

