### **6.1.2 Baseline Definition**

The baseline value for each parameter will be defined as the last observation prior to first dose of Olumacostat Glasaretil Gel, 5.0%. For subjects receiving Olumacostat Glasaretil Gel, 5.0% in ACN03/ACN04, the baseline values from ACN03/ACN04 will be considered the baseline values for calculations in ACN05. For subjects receiving Olumacostat Glasaretil Gel, Vehicle in ACN03/ACN04, baseline values will most commonly be from the Week 12/study exit visit of ACN03/ACN04. If subjects choose to enroll in this study, study procedures will not be repeated; study sites will carry over the information from the ACN03/ACN04 study to the Day 1 visit for this study.

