### **6.8.3      Clinical Laboratory Evaluation**

Laboratory data will be presented in a by-subject listing. Any clinically significant laboratory abnormalities will be captured as adverse events. Changes from Baseline in safety laboratory values will be summarized at the final follow-up evaluation using descriptive statistics for the safety population in total, as well as by treatment received in ACN03/ACN04. For subjects receiving Olumacostat Glasaretil Gel, 5.0% in ACN03/ACN04, the final follow-up analysis visit will be Week 48/ET. For subjects receiving Olumacostat Glasaretil Gel, Vehicle in ACN03/ACN04, the final follow-up analysis visit will be Week 36/ET.

Additionally, changes from Baseline in safety laboratory values will be summarized using shift tables according to normal ranges.

If repeat laboratory testing was performed to follow-up on original results, summaries will be based on original results for each visit. If repeat laboratory testing was performed due to unavailable original test results (e.g., poor sample quality, insufficient amounts, etc.) summaries will be based on repeat results for each visit.

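### The subject-level LSR summaries ignore each subject's baseline grade, so new or worsened reactions are not separated from signs that were already present

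*SAP*

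**What the plan says.** SAP 6.8.4.4 plans these LSR outputs:

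- **By-visit descriptive statistics:** "analysis visits to be summarized include Baseline and Weeks 4, 8, 12, 16, 20, 24, 28, 32, 36, 40, 44, 48".
- **Worst grade:** "Each subject's worst post-baseline grade for each LSR will also be summarized".
- **Any grade:** "the number of subjects who experience mild, moderate or severe LSRs post-baseline will be presented".
- **Listings:** "By-subject listings of all LSRs, as well as subjects with any severe LSRs will be included".

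The section has no change from baseline, no shift table and no definition of a treatment-emergent LSR. Protocol 11.5 asks only for by-visit summaries and a listing of grade 3 reactions, so it adds no baseline comparison.

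The data for one are available. SAP 6.1.2 defines a baseline for every parameter as the last value before the first dose of 5.0% gel. SAP 6.1 imports LSR grades for subjects previously on active gel ("Local skin reactions (Baseline and Weeks 4, 8, 12") and baseline LSR grades for those previously on vehicle. For the latter, "baseline values will most commonly be from the Week 12/study exit visit of ACN03/ACN04".

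Other safety measures do get a within-subject comparison. SAP 6.8.4.2 plans changes from baseline for vital signs, and SAP 6.8.4.1 plans changes and shift tables for ECG. For laboratory data, SAP 6.8.3 says that "changes from Baseline in safety laboratory values will be summarized using shift tables according to normal ranges".

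**The concern.** LSRs are the dedicated local-tolerability measure for a topical product. The natural question of a long-term table is how many subjects developed a reaction, or had one get worse, on the gel. The two subject-level summaries do not answer it, because they look only at grades after baseline.

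This study has no concurrent control arm, so the subject's own baseline is the most direct reference available within it. If a material share of subjects have some erythema, dryness, peeling, burning or itching before the first dose, the worst-grade and any-grade figures combine that background with what changed on treatment. The figures then overstate new or worsened reactions. A real worsening, such as grade 1 to grade 2, is also not distinguished from a stable grade 2.

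**Working it through.** **1. What the counting rule does.** Take three subjects whose worst post-baseline erythema grade is 1:

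| Baseline grade | Worst post-baseline grade | Planned summaries | Compared with baseline |
|---|---|---|---|
| 0 | 1 | mild LSR | new |
| 1 | 1 | mild LSR | unchanged |
| 2 | 1 | mild LSR | improved |

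The planned summaries treat all three alike. A shift table puts them in three different cells.

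**2. Whether another output fills the gap.**

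- The by-visit table shows the group at Baseline and at each visit. It gives marginal distributions and cannot show who moved.
- The listings hold every grade, but finding who worsened means reading them subject by subject, for up to 700 subjects (SAP 4.1).
- The adverse event analysis covers conditions that worsen after baseline (Protocol 9.4.7, SAP 6.8.2). Under Protocol 9.4.5, a visit-day LSR becomes an adverse event only if it is severe, while LSRs between visits are recorded as adverse events. The uncovered part is grade 1 and 2 LSRs seen on a visit day.

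**3. How large the excess can be.** The plan states no LSR rate, so there is no figure to reproduce. Protocol 1.2 reports of the dose-ranging study that "Erythema was the most common LSR", which gives no baseline prevalence. All rates below are assumptions. Let:

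- *b* = proportion with the sign at baseline
- *i* = probability of a new or worsened sign (assumed equal with and without a baseline sign)
- *r* = chance per visit that a sign which has not worsened is scored above 0 again
- *k* = number of post-baseline visits: 9 for prior-vehicle and 12 for prior-active subjects (SAP 6.1.3)
- *q* = 1 − (1 − *r*)^*k*

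Counted under the planned rule: (1 − *b*)*i* + *b*[*i* + (1 − *i*)*q*] = *i* + *b*(1 − *i*)*q*.

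Counted as new or worsened: *i*.

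Excess: *b*(1 − *i*)*q*, which can never exceed *b*.

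With *r* = 0.2, *q* = 1 − 0.8^9 = 0.866 or 1 − 0.8^12 = 0.931. With *r* = 0.5 and *k* = 9, *q* = 0.998. With *r* = 0.05, *q* is only 0.37 (9 visits) or 0.46 (12 visits).

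For 700 subjects and *k* = 9:

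| *b* | *i* = 0, *q* = 1 | *i* = 10%, *r* = 0.2 | *i* = 10%, *r* = 0.5 |
|---|---|---|---|
| 10% | 10% (70) | 17.8% (125) | 19.0% (133) |
| 30% | 30% (210) | 33.4% (234) | 36.9% (259) |
| 50% | 50% (350) | 49.0% (343) | 54.9% (384) |

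New or worsened reactions are 0 in the first results column and 10% (70 subjects) in the other two. At *i* = 10%, the excess runs from about 8 points (*b* = 10%, *r* = 0.2: 0.10 × 0.9 × 0.866 = 0.078) to 45 points (*b* = 50%, *q* = 1: 0.50 × 0.9 = 0.45). It is smaller if signs are seldom scored again.

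**The case against.** **Baseline is not absent from LSR reporting.** This stands. Baseline sits beside every later visit in the by-visit table, and all grades are listed. Severe visit-day LSRs and between-visit LSRs also reach the adverse event tables. The gap is confined to the subject-level summary of grade 1 and 2 visit-day LSRs.

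**The SAP does not call these counts drug reactions.** This also stands. A reader might infer that the plan reports pre-existing signs as reactions caused by the gel. SAP 6.8.4.4 labels the counts only as post-baseline, and the study is descriptive throughout, with no inferential testing.

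**The size is easily overstated.** A reader might infer that nearly everyone would be counted even if the gel did nothing. With 30% prevalence and independent visits, 1 − 0.7^9 = 96% and 1 − 0.7^12 = 99% would have the sign at least once. With 10% prevalence, the figures are 61% and 72%. These mainly reflect taking the worst of 9 or 12 visits. Under the same assumption, a worse-than-baseline count (sign absent, then present) would itself give 0.7 × 0.960 = 67% and 0.7 × 0.986 = 69%, or 0.9 × 0.613 = 55% and 0.9 × 0.718 = 65%. The share from subjects with a baseline sign is only 0.30 × 0.960 = 29 points, or 0.10 × 0.613 = 6 points, over 9 visits.

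**Own baseline is not the only possible reference.** The originating trials had vehicle groups. Their analysis plans are not among these documents, so it cannot be assumed that a controlled LSR comparison is missing there.

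**A baseline-referenced count has its own weakness.** A sign that arose on vehicle and persists on 5.0% gel would be classed as not worse. This is a good reason not to let the new count replace the planned tables. It is no reason to omit it.

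**Over-counting does not hide harm.** The planned figures are not too low, which limits the seriousness. They still do not separate worsening from stable signs.

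**Conclusion.** The omission is clear from the text. The SAP plans no within-subject comparison with baseline for LSRs, although the data are imported and the laboratory, ECG and vital-sign sections each have one. This makes the LSR summary less informative than it could be. It does not invalidate the study or contradict the protocol.

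The effect has a firm upper limit: the inflation from pre-existing signs is at most the baseline prevalence of the sign. Its actual size is unknown, because the documents give no baseline rates and no rates of persistence.

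Comparing the prior-active and prior-vehicle columns needs separate caution. The prior-active baseline precedes any gel, whereas the prior-vehicle baseline usually follows 12 weeks of vehicle. The groups also have up to 12 and up to 9 post-baseline visits respectively. A reader might expect a baseline-referenced table to make the columns comparable. It would not, because it uses the same baselines and the same visits.

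**What to change.** In SAP 6.8.4.4 add, for each of the five LSRs:

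1. A shift table of baseline grade by worst post-baseline grade.
2. The number and percentage of subjects whose worst post-baseline grade exceeds their baseline grade.

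Give both in total and by treatment received in ACN03/ACN04. Present them alongside the planned worst-grade and any-grade tables, which stay as they are. Add a footnote that the two prior-treatment columns differ in what preceded baseline and in the number of post-baseline visits, so they are not directly comparable.

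The cost is one additional table programmed from data already imported. No assessment, visit or study procedure changes.

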### **7. DETERMINATION OF SAMPLE SIZE**

The sample size for this study was based on the minimum requirement for a long-term safety study.

### **8. CHANGES IN THE PLANNED ANALYSES**

No changes to planned analyses.
